 - Active pouchitis, defined as a mPDAI \geq 5 and a history of \geq 4 antibiotic therapies for pouchitis in the last 12 months

or

Need for ongoing antibiotic therapy (> 4 weeks) to maintain clinical remission and a history of at least 2 attempts in the last 24 months to stop antibiotic therapy resulting in pouchitis episodes. Concomitant oral 5 ASA or local therapies containing 5-ASA (enemas, suppositories) or steroid enemas are permitted but not required but have to be stable for 4 (oral) or 2 weeks (topical) before inclusion in the study.

- Exclusion criteria
- Treatment with biologics (e.g. infliximab, adalimumab, golimumab, vedolizumab)
- Treatment with immunomodulators (azathioprine, 6-MP, methotrexate), steroids or any investigational drugs
- Use of cholestyramine
- Crohn's disease of the pouch
- Known cytomegalovirus infection of the pouch
- Clostridium difficile infection
- Isolated moderate or severe cuffitis
- Clinical significant strictures of the pouch inlet or outlet
- Concurrent intestinal obstruction
- History of familial adenomatous polyposis
- History of uncontrolled lactose intolerance
- History of confirmed (serological test and/or histology) celiac disease
- Pregnancy, breast feeding, or planning to become pregnant during the trial
- Non steroidal inflammatory medications (NSAIDs) as long-term treatment, defined as use for at least 4 days a week each month
- Dysphagia (oropharyngeal, esophageal, functional, neuromuscular)
- History of recurrent aspiration episodes
- Proven gastroparesis
- Allergy to the following generally regarded as safe ingredients (GRAS): glycerol, acid resistant HPMC, gellan gum, cocoa butter, titanium dioxide
- Adverse event attributable to previous FMT
- Allergy/intolerance to pump inhibitor therapy
- Any condition for which the investigator thinks the FMT treatment may pose a health risk (e.g. severely immunocompromised)
- Participation in another clinical trial within the last 30 days, simultaneous participation in another clinical trial, or previous participation in this trial
- During the trial period until one week after the trial end: Non-use of appropriate contraceptives in females of childbearing potential (e.g. condoms, intrauterine device {IUD}, hormonal contraception, or other means considered adequate by the responsible investigator) or in males with a child-fathering potential (condoms, or other means considered adequate by the responsible investigator during treatment

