7. OVERVIEW OF TRIAL SEQUENCE

See also study flow chart in appendix as well as study visit charts in appendix.

The trial will begin with the **screening visit (days -14 to 0).** The investigator will ask patients who are interested in participating in the study after a careful explanation, to sign an informed consent form prior to study specific examinations. The study patient will receive a copy of the consent form, which outlines the sequence of events in brief and summarizes the advantages and disadvantages of participation in the study.

After the patient has given his/her written consent, the screening examination will be performed to evaluate whether the patient is probably eligible for the study.

At the screening visit, a complete history will be taken including concomitant medication and demographic data will be collected. A physical examination will be performed and vital signs will be documented. Blood samples (max. 20 ml) will be taken from the study patient (all study patients: hematology, serum chemistry, creatinine, female study patients: urine samples for pregnancy test). Also the study patient will be provided with a stool collection kit to provide a stool sample, which should be collected at this visit or before the week 0 visit. This stool kit will also contain a sample kit for C. difficile toxin. The study patient will also be provided with a diary, which he/she will be asked to complete the diary every day in the evening during the trial. It will be also evaluated if the patient is able to swallow the oral FMT test capsule.

At least 10 days before the planned endoscopic FMT at week 0 all patients will be started on antibiotic therapy as standard of care for treatment of pouchitis. Patients on continuous antibiotic therapy will continue their regimen. Since all patients must fulfil the criteria for antibiotic pouchitis, the antibiotic with the best efficacy to treat the pouchitis episodes in the past will be used. In patients on chronic antibiotic therapy to prevent pouchitis recurrence the antibiotic regimen will be continued. 24 hours before the planned FMT the antibiotic will be discontinued.

Placebo-controlled trial period

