At phone visit 4 the coordinator will ask the study patient if adverse events occurred and review the adverse event diary. The coordinator will evaluate the clinical components of the mPDAI of the last 3 days before the phone call (stool frequency, rectal bleeding, fecal urgency/ abdominal cramping, fever) as well as the concomitant medications. If the patient is in remission according to the diary (mPDAI \leq 4) and is on no concomitant medications, a pouchoscopy will be planned for site visit 5. If the study patient is not in remission (mPDAI \geq 4) or had an early relapse after FMT the open label extension will be offered and the patient can be started on oral antibiotics again. For safety analyses a site visit 5 should be planned in the following 3-4 days. If the study patient chooses not to participate, he should be followed according the same schedule as patients who are in remission.

Early termination visit due to flare on day 1-28 after FMT or due to adverse event or patient unwillingness to continue in study necessitating early termination

If at any time between day 1-28 after endoscopic FMT the patient experiences recurrence of his pouchitis symptoms, he/she will contact the coordinator. The coordinator will ask the study patient if adverse events occurred and review the adverse event diary. The coordinator will evaluate the clinical components of the mPDAI of the last 3 days before the phone call (stool frequency, rectal bleeding, fecal urgency/ abdominal cramping, fever) as well as the concomitant medications.

If the study patient has active disease (mPDAI>4), an early termination study visit will be scheduled. A physical exam will be completed and, if possible, stool will be collected before the start of antibiotic therapy as standard of care. Blood labs will also be collected. The patient will be started on the same antibiotic, which he was on before entering the study. At the study visit the coordinator will review possible adverse events, evaluate the clinical components of the mPDAI of the last 3 days before the visit (stool frequency, rectal bleeding, fecal urgency/ abdominal cramping, fever) as well as the concomitant medications. If the patient wants to proceed into the open label study, he has to undergo at least 10 days of standard of care antibiotic therapy, before he can undergo the open label therapy with FMT (endoscopic and oral FMT).

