Dispense oral FMT or placebo Dispense omeprazole 20 mg (1 tablet) daily for 14 days during oral FMT Dispense PDAI diary Dispense adverse events diary

Pouchoscopy: Evaluation of endoscopic PDAI and perform "blinded" (real or placebo) FMT.

• Visit 2: Phone visit week 1 (7 (+1 day) days after endoscopic FMT /placebo and on oral FMT/placebo)

Formal aspects:

Adverse events (review adverse events diary)

Concomitant medication

Calculation of clinical mPDAI (stool frequency, rectal bleeding, fecal urgency/abdominal cramping, fever)

• Visit 3: Site visit week 2 (15 +3 days after endoscopic FMT /placebo and on oral FMT/placebo)

Formal aspects:

Adverse events (review adverse events diary)

Concomitant medication

Calculation of clinical mPDAI (stool frequency, rectal bleeding, fecal urgency/abdominal cramping, fever)

Reminder stool collection on day 15, 16 or 17 (day 1-3 after end of oral FMT) and bring in stool.

• Visit 4: Phone visit week 4 (2-3 days before planned week 4 site visit)

Formal aspects:

Adverse events (review adverse events diary)

Concomitant medication

Reminder to bring stool day 25, 26 or 27.

Calculation of clinical mPDAI (stool frequency, rectal bleeding, fecal urgency/abdominal cramping, fever)

If patient is in clinical remission (mPDAI ≤ 4) and no need for antibiotics plan for pouchoscopy week 4

If patient is not in clinical remission (mPDAI > 4) or need for antibiotics or comes in due to exacerbation of symptoms with possibility to continue with open label extension. Need to restart 10 day course of antibiotics as standard of care similar to initial antibiotic treatment before the first FMT

• Visit 5: Site visit Week 4 (day 28 +/- 3 days after first transplant) or early termination visit due to flare (day 1-28 after first transplant)

Examinations

Vital signs: blood pressure (mm Hg), heart rate (min-1), weight (kg), temperature

Physical examination:

- Head (including ENT and eyes)
 Lymphatic system
 Endocrine system
 Lungs and respiratory tract
 Peripheral vascular system
 Skin and connective tissue
- Cardiovascular system

- Other

each: actual status: Present finding / normal condition / not examined

Measurement of laboratory parameters

Hematology Serum chemistry

Stool collection: Bring to visit.

Formal aspects:

Return of study medication (empty containers)

Compliance assessment (count of empty containers returned)

Concomitant medication

Adverse events (review adverse events diary)

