Formal aspects:

Adverse events

Concomitant medication

Calculation of clinical mPDAI (stool frequency, rectal bleeding, fecal urgency/abdominal cramping, fever)

Stool collection: Stool collection

• Visit 9: Phone visit week 24 (168 +/- 10 days after first transplant)

Formal aspects:

Review if serious adverse events occurred in previous 8 weeks

10. FOLLOW UP VISITS OF PATIENTS PARTICIPATING IN OPEN LABEL EXTENSION AFTER WEEK 4

• Visit 6OL: Site visit week 6 (week 0 OL)

This visit should be performed after the patient completed at least 10 days of antibiotics

Examinations

Vital signs: blood pressure (mm Hg), heart rate (min-1), weight (kg)

Physical examination:

- Head (including ENT and eyes)
- Lymphatic system
- Endocrine system
- Lungs and respiratory tract
- Peripheral vascular system
- Cardiovascular system

- Gastrointestinal tract, liver, spleen
- Urogenital system
- Nervous system
- Muscular and skeletal system
- Skin and connective tissue
- Other

each: actual status: Present finding / normal condition / not examined

Formal aspects:

Concomitant medication Calculation of mPDAI score (before pouchoscopy) Dispense oral FMT capsules Dispense omeprazole 20 mg (1 tablet) daily for 14 days during oral FMT Dispense PDAI diary Dispense adverse events diary for OL follow-up phase

Blood sampling and measurement of laboratory parameters (be performed in the 24 hours before FMT)

- Urine pregnancy test

Pouchoscopy: Evaluation of endoscopic PDAI and perform FMT.

• Visit 7OL: Phone visit week 7 (week 1 OL; 7 days (+1 day) after second transplant)

Formal aspects:

Adverse events (review adverse events diary)

Concomitant medication

Calculation of clinical mPDAI (stool frequency, rectal bleeding, fecal urgency/abdominal cramping, fever)

• Visit 8OL: Site visit week 8 (week 2 OL, 15 + 3 days after second transplant)

Formal aspects:

Adverse events (review adverse events diary)

Concomitant medication

Calculation of clinical mPDAI (stool frequency, rectal bleeding, fecal urgency/abdominal cramping, fever)

Reminder stool collection on day 15, 16 or 17 (day 1-3 after end of oral FMT) and bring in stool. Plan for pouchoscopy visit 9OL

• Visit 9OL: Site visit week 10 (week 4 OL, 28 +/- 3 days after second transplant)

Examinations

Vital signs: blood pressure (mm Hg), heart rate (min-1), weight (kg)

Physical examination:

- Head (including ENT and eyes)
- Lymphatic system
- Endocrine system

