The "adverse events diary" will assess for adverse events during the FMT phase (14 days) and daily for 28 days after the last day of oral FMT.

^c Visit 4: Start of pretransplant antibiotic therapy for 10-14 days only in patients qualifying for open label extension

^d Clinical mPDAI.

^e Stool samples for microbiome, calprotectin and C. diff analyses.

^fStool samples for calprotectin and microbiome analyses.

[figure not shown]
^g between visit 1-5 or visit 6-8 or visit week 6OL-12OL

^h Endoscopic open label FMT followed by oral FMT only if no clinical remission according to mPDAI at visit 4 and study patients wants to continue in open label FMT.

¹ Evaluation of serious adverse events occurring in the follow-up period

^jCollect adverse event diary

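### No C. difficile result or eligibility re-check is required before the open-label FMT at visit 6OL, although C. difficile infection is an exclusion and is tested for before the first FMT

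*Combined protocol and SAP*

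**What the plan says.** Section 6 lists "Clostridium difficile infection" among the exclusion criteria. Section 7 gives the patient a stool kit at screening and adds: "This stool kit will also contain a sample kit for C. difficile toxin". The sample is due at screening or before week 0. Section 8 repeats the toxin test under the screening visit. Footnote e of the visit chart (section 21), attached to the screening stool, reads "Stool samples for microbiome, calprotectin and C. diff analyses". Visit 1 then includes a check of all eligibility criteria before randomization.

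For a patient who flares, section 7 has the coordinator score the clinical mPDAI items and schedule an early termination visit, where "if possible, stool will be collected before the start of antibiotic therapy as standard of care". It continues: "The patient will be started on the same antibiotic, which he was on before entering the study". The visit 5 list in section 8, which also serves as the early termination list, has "Stool collection: Bring to visit" and names no assay.

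For visit 6OL, section 10 states: "This visit should be performed after the patient completed at least 10 days of antibiotics". The listed content is vital signs, physical examination, concomitant medication, mPDAI, dispensing, a urine pregnancy test, and pouchoscopy with FMT. Section 7 adds a review of adverse events. The list has no stool sample, no C. difficile test and no eligibility check.

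**The concern.** The exclusion is applied with a laboratory test before one transplant and, on the readable text, not before the other. The patients who reach the second transplant are those in whom the question arises most naturally. They have symptoms, and they have recently had antibiotics, which section 3 itself names as a C. difficile risk. Their flare is defined by stool frequency, bleeding, urgency or cramps, and fever, none of which identifies a cause. Under chart footnote a, those who join the extension have no visit 5 pouchoscopy.

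A C. difficile episode could therefore be handled as a pouchitis flare, put back on the earlier antibiotic, and diagnosed late. It could also be missing from the adverse events, in a trial whose primary endpoint is safety. Section 3 describes FMT as effective in C. difficile colitis, so an unrecognized case that improved could be scored as an open-label pouchitis remission.

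**Working it through.** **1. The plan's own figures.** Section 20 (Microbiome Analyses) assumes 9 patients in remission and 11 entering the extension: 9 + 11 = 20, and 11/20 = 55%. The stated power (80% for 10% against 77.5%, 10 per arm, two-sided Fisher exact test at 0.05) comes out at 80.2% by full enumeration. It plays no part in this point.

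**2. The two transplants side by side.**

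| | First FMT (visit 1) | Open-label FMT (visit 6OL) |
|---|---|---|
| Antibiotics beforehand | at least 10 days | at least 10 days |
| Pregnancy test | yes | yes |
| Pouchoscopy | yes | yes |
| Eligibility check listed | yes | no |
| C. difficile toxin result | sample from screening to week 0 | none in readable text |

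One exclusion, pregnancy, is re-tested before the second FMT. C. difficile is not. Section 11 names no C. difficile test, but it omits the screening test too, so its silence is not evidence either way.

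**3. What each stool sample is for (section 21).**
- Screening: footnote e, which includes C. difficile.
- Visits 3 and 4: footnote f, calprotectin and microbiome only.
- Visit 5: marker g. Footnote g reads "between visit 1-5 or visit 6-8 or visit week 6OL-12OL", a set of visit ranges rather than a stool analysis. The marker may be a fault in the readable copy of the chart.
- Early termination: stool collected, no marker.
- Visit 6OL: no stool sample.
- Visit 8OL, after the second FMT: footnote f.

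The gap at visit 6OL does not depend on marker g. The gap at visit 5 does, in part. The visit 5 list in section 8 names no C. difficile assay, whereas the screening list in the same section does.

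**4. Age of the last known result at the open-label FMT.** The chart puts that FMT on day 38. The named sample falls between day -14 and day 0.
- If it is the only test: 38 - 0 = 38 days to 38 - (-14) = 52 days. The comparable maximum before the first FMT is 0 - (-14) = 14 days.
- If the visit 5 stool (day 28) is in fact tested: 38 - 28 = 10 days.
- If a patient flares on day 1 and completes 10 antibiotic days, the second FMT could come at about day 1 + 10 = 11, which is 11 days after a day 0 sample.

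The age could thus be anywhere from about 10 to 52 days, depending on a marker that cannot be read with confidence and on when the flare occurs.

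**5. Scale.** The documents give no C. difficile rate. For orientation only, with an assumed risk r per entrant, the chance of at least one case among 11 is 1 - (1 - r)^11:
- r = 1%: 10%
- r = 2%: 20%
- r = 5%: 43%
- r = 10%: 69%

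These are assumptions, not estimates.

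**The case against.** The strongest reply is that the stool that matters is the one at visit 5 or early termination, and its chart marker is unreliable. A reader might infer that C. difficile is tested exactly once and that every result is 38 to 52 days old at the second FMT. The documents do not establish that. Marker g also sits on entries it does not fit, such as the capsule dispensing at visit 6OL, and a figure is missing next to the footnotes. What stands is narrower: no readable text assigns the assay, and none makes a negative result a condition of the open-label FMT.

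A reader might also infer that nothing scheduled could reveal an infection. That goes too far. The flare visit has an examination and blood tests. The adverse event diary asks about fever, diarrhea, abdominal pain and blood in stool. Section 14 requires each adverse event to be followed until it resolves or is explained. Visit 6OL has an examination and a pouchoscopy. Investigators may stop a patient's participation or order a clinically indicated test. These steps may raise suspicion, but none is a C. difficile test, and the visit 6OL pouchoscopy comes only after at least 10 days of antibiotics.

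It is also fair to say that these patients qualify through long or repeated antibiotic use. The documents therefore do not show that the trial's courses raise their C. difficile risk above usual care. That objection stands, and the point does not need the claim.

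**Conclusion.** The point holds as an optional, inexpensive safety improvement. The plan tests for an excluded infection before the first FMT and, on the readable text, requires neither a C. difficile result nor an eligibility re-check before the second. The stake is delayed diagnosis among about 11 planned extension patients, together with possible misclassification in exploratory extension outcomes. Most flares will presumably be ordinary pouchitis relapse, and the number of infections cannot be estimated.

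Two stronger conclusions might be drawn and are not supported. The first is that the efficacy comparison is compromised: week 4 status is settled before the open-label FMT, and the week 8 and 16 endpoints exclude extension patients, so the randomized comparison is unaffected. The second is that giving FMT to an infected patient is itself hazardous: sections 3, 4 and 13 describe FMT in C. difficile as effective and safe. The worry is a missed or late diagnosis.

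The conclusion assumes that the visit 5 footnote, if restored, does not already specify the assay. Even if it does, the requirement for a negative result before visit 6OL would still need to be written down.

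**What to change.** 1. For patients heading to the extension, run C. difficile toxin on the visit 5 or early termination stool, taken before antibiotics restart where possible. Correct the chart marker to say so.
2. If that sample was missed, obtain one before visit 6OL.
3. Add a negative C. difficile result to the conditions for the open-label FMT.
4. If the result is positive, treat the infection, record it as an adverse event, and defer or withhold the open-label FMT. Keep the patient in follow-up on visits 6-9, the schedule section 7 already gives to patients who decline the extension. Using the premature withdrawal route listed under visit 5 would lose safety data in a 20-patient trial.

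The cost is about 11 assays, one per planned entrant and mostly on stool already collected, plus a few extra samples. The downside is an occasional delayed or withheld FMT, including after a false-positive result.

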14. DOCUMENTATION AND REPORTING OF ADVERSE EVENTS

The study patients will be instructed to contact the investigator, if any serious or unexpected AE occurs, so that appropriate action can be taken.

Moreover, the investigator must ask at each follow-up visit a generally worded question without searching for any special symptoms, e.g. "Has your state of health worsened since we last met?" If the answer to this question is "no", no further questions will be asked. If the answer to the question is "yes", the investigator will document the nature, time, severity, seriousness and duration as well as the causality of the AE. For each AE a specific AE documentation form will be provided, which should be completed by the PI as an initial report. The report must contain a detailed description of the symptoms observed and the concomitant treatment administered. Furthermore, the investigator must comment on a possible causative relationship between the AE and the trial medication. Each AE must be followed until it is resolved or can be explained satisfactory.

The following has to be documented for each AE:

- Nature of the event
- Time of onset: date, time
- Concomitant treatment: product (generic name), indication, dosage, dosage interval, presentation, mode of administration, administration regimen
- Duration of the AE
- Severity
- Seriousness
- Causality
- Outcome

Severity

The severity is evaluated as follows:

- 1. Mild: event/symptom does not interfere with normal daily activities
- 2. Moderate: event/symptom interferes with normal daily activities

3. Severe: - event/symptom prevents normal daily activities

Causality

The relationship between an AE and the study medication is classified according to the WHO classification:

Certain

A clinical event, including laboratory test abnormality, is occurring in a plausible time relationship to drug administration, and which concurrent disease or other drugs or chemicals cannot explain. The response of the study patient to withdrawal of the drug should be clinically plausible. The event must be definite pharmacologically or phenomenologically, using a satisfactory rechallenge procedure if necessary.

Probable/Likely

A clinical event, including laboratory test abnormality, with a reasonable time sequence to the administration of the drug, unlikely to be attributed to concurrent disease or other drugs or chemicals, and which follows a clinically reasonable response on withdrawal (de challenge). Rechallenge information is not required to fulfil this definition.

Possible

A clinical event, including laboratory test abnormality, with a reasonable time sequence to administration of the drug, but which could also be explained by concurrent disease or other drugs or chemicals. Information on drug withdrawal may be lacking or unclear.

Unlikely

A clinical event, including laboratory test abnormality, with a temporal relationship to drug administration which makes a causal relationship improbable, and in which other drugs, chemicals or underlying disease provide plausible explanations.

Conditional/Unclassified

A clinical event, including laboratory test abnormality, reported as an adverse reaction, about which more data are essential for a proper assessment or the additional data are under examination.

Not assessable / Unclassifiable

A report suggesting an adverse reaction, which cannot be judged because information is insufficient or contradictory, and which cannot be supplemented or verified.

As an alternative to the above-mentioned WHO assessments, the following assessment can be made:

Not related

There is sufficient information available to show that the etiology is unrelated to the study medication.

Measures at the onset of adverse events

Measures at the onset of adverse events are classified and described as follows:

- 1) None, i.e. the study medication was not changed
- 2) The dose of the study medication was reduced
- 3) The study medication was withdrawn and/or
- 4) Other measures (clear text)

The course and outcome of the adverse event will be commented on as follows:

- Recovered without sequelae
- Not yet recovered
- Recovered with sequelae
- Fatal
 - Documentation and Reporting of Serious Adverse Events

On enrolment in the study, the study patients will be instructed to contact the investigator if a serious or unexpected AE occurs, so that appropriate measures can be taken.

Any SAE (including death, irrespective of the cause) occurring during or for up to 14 days after the end of the study will be immediately reviewed by the PI, i.e. within 24 hours.

A specific SAE documentation form will be provided. In case of an SAE, this form will be completed and reviewed by the PI as an initial report, and if the SAE is judged to be possible related or related to study drug will be sent (via fax) to the IRB of the University of North Carolina. The report must contain a detailed description of the symptoms observed and the concomitant treatment administered. Furthermore, the investigator must comment on a possible causative relationship between the AE and the trial medication. Each SAE must be followed until it is resolved or can be explained satisfactorily.

The general procedure for the observation, collection and analysis of drug risks (regulatory affairs) in conformity with the appropriate national Drug Law shall apply without qualification.

In accordance with drug safety and national requirements, the study PI will inform the IRB of the study at the University of North Carolina and will make sure that the involved persons will obtain adequate information.

The following instructions must be heeded:

In the case of an intolerable SAE, the study patient must, at the decision of the investigator, be withdrawn from the clinical trial, and symptomatic treatment must be administered. The measures taken must be recorded on the CRF.

In accordance with local legislation, the investigators will submit copies of the final SAE-report to the Regulatory Authorities concerned, if necessary.

15. ABNORMAL LABORATORY RESULTS

All laboratory values outside of the normal range will be repeated as judged appropriate to ensure the validity of the abnormal result. The investigator will document all laboratory values on the relevant page of the CRF and will assess the etiology of the clinically relevant abnormal laboratory values.

Clinically relevant abnormal laboratory values are only documented on the AE form of the CRF, if the study patient is discontinued, hospitalized, or, in the investigator's opinion, it should be considered as an AE.

Abnormal laboratory results caused by ulcerative colitis should not be reported on the AE form.

